13.13.3. Inferential statistics

For the primary endpoint (complication rate of the EVA Nexus), a one-sample proportion test will be performed to test whether the obtained rate is different from rates found in the literature (30%, 15% and 5%).

For the remaining data (demographics and secondary objectives), group comparisons (no complications vs complications) of count variables will be analyzed using a Fisher's exact test and group comparisons (no complications vs complications) of continuous variables will be performed using the T-test or the Wilcoxon signed rank test, as appropriate (=when the normality of the residuals and the equality of the variances are met, the T-test will be used, and when the normality of the residuals or the homoskedasticity of the variances will not be met, the Wilcoxon signed rank test will be used). Last, in order to test a first predictive model, a logistic or Poisson regression, as appropriate, with backward selection method will be performed, starting with all variables associated with the target with a p-value lower than 0.1. The final model will contain variables associated with the outcome with a p-value lower than 0.05.

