To evaluate possible (S)AE that may be related to the use of the surgical platform.	Rarely, adverse events that are related to the surgery may only become visible the day after the surgery. A typical example is a choroidal hemorrhage, which is related to variations in intraocular pressure during the surgery. Hence, standard as in the standard-of care, a postoperative check of the eye at the day after the surgery will be performed to determine the presence of such AE's.
To evaluate the impact of usage of the EVA NEXUS on the surgical parameters used during the procedure	
The surgical parameters include a range of data collected on the following:
 
Aspiration Irrigation / Infusion BSS Usage Vitrectomy Ultrasound Illumination Diathermy Micro-injection Silicone oil injection / extraction Laser

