8. CLINICAL INVESTIGATION POPULATION

8.1. Number of participants – sample size analysis

With a complication rate ranging from 5% up to 30% in previous studies, we have no a priori about the complication rate of the EVA Nexus system. We therefore consider a rather conservative hypothesis and expect to have around 5% of complications with the EVA Nexus system. We plan recruit 250 patients in total in order to get at least 10 complications with EVA Nexus. The estimated enrolment time is 6 months.

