13. STATISTICS

13.1. Description of statistical methods

Will be outsourced to a licensed medical statistician (Ars Statistica). An pseudonymizedExcel-export will be generated from the eCRF for statistical analysis.

For the primary endpoint (complication rate of the EVA Nexus), a one-sample proportion test will be performed to test whether the obtained rate is different from rates found in the literature (30%, 15% and 5%).

For the remaining data (demographics and secondary objectives), group comparisons (no complications vs complications) of categorical variables will be analyzed using a Fisher's exact test and group comparisons (no complications vs complications) of continuous variables will be performed using the T-test or the Wilcoxon signed rank test, as appropriate (=when the normality of the residuals and the equality of the variances are met, the T-test will be used, and when the normality of the residuals or the homoskedasticity of the variances will not be met, the Wilcoxon signed rank test will be used). Last, in order to test a first predictive model, a logistic or Poisson regression, as appropriate, with backward selection method will be performed, starting with all variables associated with the target with a p-value lower than 0.1. The final model will contain variables associated with the outcome with a p-value lower than 0.05.

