13.3. The level of statistical significance

For all analyses, the level of significance will be 5% two-sided significant level.

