14.5 Statistical Analysis plan

13.13.1. Descriptive statistics

Summary statistics (Nb observations, minimum, Q_{25} , median, Q_{75} , maximum, standard deviation) of the whole studied group will be provided.

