Date of Death (D-M-Y)  Today D-M-Y [Add Field](#) [Add Matrix of Fields](#)

    Variable: event_date_of_hospitalization Branching logic: [sae_reasons(4)] = '1'  How to embed a field elsewhere

Date of hospitalization  Today Y-M-D [Add Field](#) [Add Matrix of Fields](#)

    Variable: event_date_of_discharge Branching logic: [sae_reasons(4)] = '1'  How to embed a field elsewhere

Date of discharge  Today Y-M-D [Add Field](#) [Add Matrix of Fields](#)

    Variable: name_of_device Branching logic: [did_any_event_occur] = 1  How to embed a field elsewhere

Name of study device [Add Field](#) [Add Matrix of Fields](#)

    Variable: event_device_related Branching logic: [did_any_event_occur] = 1  How to embed a field elsewhere

Was the event device related? Not related Unlikely Possibly Probably Definitely [reset](#) [Add Field](#) [Add Matrix of Fields](#)

    Variable: event_procedure_related Branching logic: [did_any_event_occur] = 1  How to embed a field elsewhere

Was the event study-procedure related? Yes No Not applicable [reset](#) [Add Field](#) [Add Matrix of Fields](#)

    Variable: name_of_procedure_ae Branching logic: [event_procedure_related] = 1  How to embed a field elsewhere

Name of study procedure A study-specific procedure, performed outside the standard of care [Add Field](#) [Add Matrix of Fields](#)

    Variable: event_action_taken Branching logic: [did_any_event_occur] = 1  How to embed a field elsewhere

Was any action taken? None Medication Non-drug therapy Surgery/Procedure Hospitalization Stop study due to AE Further investigation / other [Check all that apply](#) [Add Field](#) [Add Matrix of Fields](#)

    Variable: event_other_action Branching logic: [event_action_taken(7)] = '1'  How to embed a field elsewhere

Specify further investigation or other: [Add Field](#) [Add Matrix of Fields](#)

     Variable: *action_study_intervention* Branching logic: *[did_any_event_occur] = 1* [How to embed a field elsewhere](#)

Was action taken regarding study intervention

None
 Temporarily interrupted
 Stopped permanently
 Other

[reset](#)

[Add Field](#) [Add Matrix of Fields](#)

     Variable: *other_actinn_intervention* Branching logic: *[action_study_intervention] = 6* [How to embed a field elsewhere](#)

Other

[Expand](#)

[Add Field](#) [Add Matrix of Fields](#)

     Variable: *event_outcome* Branching logic: *[did_any_event_occur] = 1* [How to embed a field elsewhere](#)

Outcome of the event

Recovered

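### The Fisher test named for the secondary (S)AE objective compares patients who all had EVA Nexus surgery, so it does not test whether (S)AEs are related to the platform

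*Combined protocol and SAP*

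**What the plan says.** The secondary objectives table in Section 6 includes: "To evaluate possible (S)AE that may be related to the use of the surgical platform". Its parameter is the routine eye check on the day after surgery.

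The inferential plan for this objective is one shared rule. Section 13.1 has: "For the remaining data (demographics and secondary objectives), group comparisons (no complications vs complications) of categorical variables will be analyzed using a Fisher's exact test". Section 13.13.3 (under 14.5, Statistical Analysis plan) repeats it with one word changed: "For the remaining data (demographics and secondary objectives), group comparisons (no complications vs complications) of count variables will be analyzed using a Fisher's exact test". For all analyses, "the level of significance will be 5% two-sided significant level" (13.3).

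The descriptive part, 13.13.1, reads: "Summary statistics (Nb observations, minimum, Q_{25} , median, Q_{75} , maximum, standard deviation) of the whole studied group will be provided".

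Relatedness to the device is recorded for each event. The Appendix C form asks: "Was the event device related? Not related Unlikely Possibly Probably Definitely". Sections 18.3 and 18.3.1 require the same causality assessment.

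**The concern.** Every patient in the analysis had surgery with the EVA Nexus, so exposure to the platform does not differ between the two groups. The null hypothesis of the test is that a day-1 (S)AE is independent of having had a complication. That is a different statement from the platform causing no (S)AE.

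A link between complications and day-1 events that has nothing to do with the machine is plausible from the protocol itself. Section 9.1 names high myopia, very small eyes and earlier trauma as raising the risk of adverse events. The flowchart in 7.2 records pre-operative conditions known to affect their incidence. Such eyes could show more of both.

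Device safety is the stated purpose of the study. A p-value placed under this objective could be misread in either direction: a small one as a signal about the platform, a large one as reassurance.

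**Working it through.** **1. The plan's own figure.** Section 8.1 says "We plan recruit 250 patients in total in order to get at least 10 complications with EVA Nexus" and the investigators "expect to have around 5% of complications with the EVA Nexus system". Expected complications are 250 × 0.05 = 12.5. With X ~ Binomial(250, 0.05), P(X ≥ 10) = 80.5%, and the smallest N giving 80% is 249. So 250 reproduces at about 80% probability; 95% would need 311. The Fisher comparison therefore sets about 12 patients against about 238.

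**2. Does another planned analysis cover the objective?**
- The one-sample test against 30%, 15% and 5% (13.13.2) concerns the complication rate only.
- The comparison with historical DORC EVA data (Sections 6 and 7.1) is named for intra-operative adverse events, complications and device issues, not for day-1 (S)AEs.
- The regression in 13.13.3 is a predictive model within the same cohort.
- The statistics in 13.13.1 include no proportion and no interval. For a yes/no event in fewer than 25% of patients, the minimum, lower quartile, median and upper quartile are all 0.

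**3. What drives the Fisher test.** *Complications* is read here as the intra-operative events of Appendix A. Let m be the number of patients with a complication, m ~ Binomial(250, 0.05). Let p1 and p0 be the day-1 (S)AE rates with and without a complication. Then

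P(reject) = Σ_m P(m) Σ_a Σ_b Bin(a; m, p1) · Bin(b; 250 − m, p0) · 1[two-sided Fisher p ≤ 0.05].

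The documents give no day-1 rate beyond saying that such events are rare, so all p1 and p0 below are assumptions.

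*No platform effect; any difference comes from harder operations:*

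| p0 | p1 | P(reject) |
|---|---|---|
| 2% | 2% (no link) | 1.7% |
| 2% | 5% | 8.8% |
| 2% | 10% | 27.2% |
| 2% | 20% | 63.8% |
| 1% | 5% / 10% / 20% | 13.7% / 35.9% / 71.8% |
| 5% | 10% / 20% / 30% | 10.6% / 41.4% / 70.5% |

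*Platform harm present, under different mechanisms:*

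| Mechanism | Rates | P(reject) |
|---|---|---|
| Total rate equal in both groups, no other link | 4% / 10% / 20% | 2.0% / 2.5% / 3.0% |
| Harm multiplies existing risk ×1 / ×2 / ×3 | from 20% vs 2% | 63.8% / 90.4% / 98.4% |
| Harm adds 0 / 2 / 5 / 10 points to both groups | from 20% vs 1% | 71.8% / 61.3% / 51.8% / 42.6% |
| Harm acts by raising complications to 5% / 10% / 15% | 20% vs 1% | 71.8% / 92.4% / 97.9% |

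The equal-rates row is the Fisher null by construction, so its 2–3% is the size of the test and not a finding about power in general. With more harm, rejection can stay flat, rise or fall, depending on the mechanism. It can also be high with no harm at all.

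**4. What a direct estimate would give.** The exact (Clopper-Pearson) upper 95% limit for x of n is the 0.975 quantile of Beta(x + 1, n − x). At n = 250:
- 0 affected patients: 0 to 1.5% (upper limit 1 − 0.025^(1/250) = 1.46%)
- 5 affected: 0.7% to 4.6%
- 10 affected: 1.9% to 7.2%

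**The case against.** The objective is worded as an evaluation, and its parameter is the presence of events on day 1. No null hypothesis about the platform is stated, and nothing says that a significant Fisher result will be read as a platform effect. That is fair: misreading is a risk, not a planned conclusion. It still leaves the only group test attached to this objective answering another question.

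A reader might infer three stronger things that the documents do not support:
- *The test rejects falsely when the platform is harmless.* This needs a link between complications and day-1 (S)AE. With none, rejection is below 5%; with a weak one (5% versus 2%) it is 9%. The documents give neither a rate nor a link.
- *The test has almost no power when the platform is harmful, or fires less as harm grows.* The first needs harm spread equally with no other link. The second needs harm that adds equally to both groups; it reverses when harm multiplies existing risk or acts through complications.
- *No output would show the (S)AE rate, and the relatedness grade goes unused.* An overall count can be read from the margins of the Fisher table, and the grade could be tabulated under the same rule. Causality is assessed per event (18.3.1), SAEs are evaluated and listed (18.5, 18.6), and the data will be tabulated for the final report (16.1). What is missing is a specified proportion, an interval and a summary of device-related events.

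The reading of *complications* as intra-operative is also an inference from Sections 6 and 7.1 and Appendix A. Appendix A lists choroidal hematoma and subchoroidal hemorrhage, while Section 6 gives choroidal hemorrhage as its day-1 example. If day-1 events also define the complication group, the simple model above does not apply and the comparison becomes partly circular.

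**Conclusion.** The point holds in a limited form. The Fisher test by complication status does not test whether (S)AEs are related to the platform, and neither a significant nor a non-significant result is informative on that. This conclusion follows from the single-device cohort and needs no assumed rate. The size of the problem does: with no platform effect, 250 patients and 5% complications, rejection runs from about 2% (no link) to 64% (20% versus 2%). All of these event rates are assumptions. The primary endpoint is untouched. This should be corrected because it assigns an unsuitable analysis to a safety objective when the data for a suitable one are already collected.

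**What to change.** In 13.1 and 13.13.3, take the (S)AE objective out of the complications versus no complications rule. In its place, report over all EVA Nexus patients in the analysis:
- the number and proportion with at least one day-1 (S)AE;
- the number and proportion with at least one day-1 (S)AE graded possibly, probably or definitely device related on the Appendix C form;
- an exact 95% confidence interval for each.

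Interpret both as estimates. State that there is no concurrent comparator for day-1 (S)AEs and that relatedness is graded by an investigator who knows the device. State also which events define the complication group. If the cross-tabulation by complication status is kept, label it as descriptive of complicated and uncomplicated operations and not as evidence about the platform.

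The cost is a few lines of SAP wording and one small table, with no new data, patients or visits. Section 13.7 leaves the statistical plan open until it is agreed before data lock. The downside is that an estimate with an interval replaces a p-value, and it does not by itself attribute events to the platform.

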11. CLINICAL INVESTIGATION ASSESSMENTS

11.1. Subject Characteristics

During vitrectomy surgery, typical surgical parameters will be recorded:

- Surgical indication
- If combined phaco-surgery is performed: amount of phaco power used
- Staining dyes (if used)
- Amount of laser coagulates (if used)
- Type of tamponade left in the eye: BSS+ liquid, air bubble, air, gas (type + concentration) or silicone oil (type)

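### The two-group test rule names a paired test for independent groups, sends unequal-variance data to a rank test that does not hold 5%, and is inconsistent about which variables go to Fisher's test

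*Combined protocol and SAP*

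**What the plan says.** Sections 13.1 and 13.13.3 of the combined protocol and SAP carry nearly the same paragraph on demographics and secondary objectives. Patients with a complication are compared with those without.

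- **Continuous variables.** A t-test is used if the residuals are normal and the variances equal. If normality fails "or the homoskedasticity of the variances will not be met, the Wilcoxon signed rank test will be used". Both sections say this. Neither mentions Welch's t-test.
- **Other variables.** Section 13.1 reads "group comparisons (no complications vs complications) of categorical variables will be analyzed using a" Fisher's exact test. Section 13.13.3 reads "group comparisons (no complications vs complications) of count variables will be analyzed using a" Fisher's exact test.
- **Use of the results.** Variables with p below 0.1 enter a backward-selected regression.
- **Level.** Section 13.3: "For all analyses, the level of significance will be 5% two-sided significant level".

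Section 11.1 lists a variable that is a true count: "Amount of laser coagulates (if used").

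**The concern.** Three things in this rule do not work as written.

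1. The signed rank test analyses differences within pairs. Here each patient belongs to one of two separate groups of different size, so there are no pairs.
2. Failing equal variance alone is enough to trigger the rank test. Normal data with unequal spread therefore go to a test whose null distribution assumes identical distributions in the two groups. The smaller group dominates the variability of the rank statistic, so a difference in spread moves the rejection rate away from 5%, upward or downward depending on which group is more variable.
3. The two sections disagree on which variables go to Fisher's test. Applied to a count with many distinct values, Fisher's test treats each value as an unordered category and discards the ordering.

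At stake are the secondary comparisons and the p < 0.1 screen, where a null variable can be admitted too often and a real predictor missed. With about a dozen events expected, the model has little room for either.

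**Working it through.** **Group sizes.** Section 8.1: "We plan recruit 250 patients in total in order to get at least 10 complications with EVA Nexus", and the investigators "expect to have around 5% of complications with the EVA Nexus system". 250 × 0.05 = 12.5 expected complications, and the binomial probability of at least 10 is 0.805. So 250 fits the stated aim at about 80% assurance (the plan states no assurance level). This gives about 12 versus 238. Section 8.1 also says "With a complication rate ranging from 5% up to 30% in previous studies": 15% gives 37.5, about 38 versus 212, and 30% gives 75 versus 175.

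**Step 1: the named test.** Given 12 unpaired values and 238 unpaired values, the signed rank test cannot be computed; software stops with a shape error. From here the two-sample rank-sum test stands in for it.

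**Step 2: rank-sum under unequal variances.** The documents give no SDs, so the ratios are assumptions. Data are normal with equal means; the test is two-sided at 0.05.

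A closed form shows the mechanism. Let m and n be the smaller and larger group sizes and s the SD ratio (smaller group over larger). Put

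- a = arcsin(s²/(1+s²))/(2π)
- b = arcsin(1/(1+s²))/(2π)

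The true variance of the rank statistic, divided by the variance the test assumes, is

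k = [(n−1)a + (m−1)b + 0.25] / [(m+n+1)/12],

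and the size is about 2 × [1 − Φ(1.96/√k)].

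- s = 2, 12 versus 238: a = 0.1476, b = 0.0320. k = (237 × 0.1476 + 11 × 0.0320 + 0.25)/20.92 = 1.70, √k = 1.304, 1.96/1.304 = 1.503, size 13.3%.
- s = 0.5: a and b swap. k = (237 × 0.0320 + 11 × 0.1476 + 0.25)/20.92 = 0.453, √k = 0.673, 1.96/0.673 = 2.91, size 0.36%.

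Simulation with 20,000 runs per cell agrees:

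| Split | SD ratio | Rank-sum | Welch | Student's t |
|---|---|---|---|---|
| 12 v 238 | 0.5 | 0.3% | 5.3% | 0.0% |
| 12 v 238 | 1 | 5.0% | 5.2% | 5.1% |
| 12 v 238 | 1.5 | 9.8% | 4.8% | 16.8% |
| 12 v 238 | 2 | 13.4% | 4.9% | 28.6% |
| 12 v 238 | 3 | 17.2% | 5.1% | 43.8% |
| 38 v 212 | 2 | 11.6% | 4.9% | 20.8% |
| 75 v 175 | 2 | 9.2% | 5.0% | 12.4% |

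A further independent run gave 13.7% and 0.35% for rank-sum at ratios 2 and 0.5 (12 versus 238), which is within simulation error.

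The whole two-stage rule was also simulated at 12 versus 238, with Shapiro and Levene as assumed pre-tests (4,000 runs). It rejects 0.4%, 5.2%, 14.4% and 17.1% at ratios 0.5, 1, 2 and 3. At ratio 2 it sends 86% of datasets to the rank test.

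**Step 3: the p < 0.1 screen.** At 12 versus 238, a null variable with doubled SD in the complication group passes 21.4% of the time by rank-sum and 10.0% by Welch. With halved SD, rank-sum passes 1.4%. For a real shift of 0.5 SD (SD of the larger group) with halved SD in the complication group, power at 5% is 54% for rank-sum and 84% for Welch.

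**Step 4: Fisher on counts.** At 12 versus 238, with assumed distributions and 5,000 runs (Monte Carlo p-values):

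| Counts compared | Fisher power | Rank-sum power |
|---|---|---|
| Poisson 3.5 v 2 | 80% | 82% |
| Poisson 13 v 10 | 60% | 82% |
| Negative binomial 400 v 200 (k = 2) | 23% | 82% |

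With no true difference, Fisher rejected 4.3% (Poisson 2), 5.7% (Poisson 10) and 3.6% (negative binomial 200). The test is exact, so 5.7% is simulation noise.

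**Step 5: is Welch safe for everything?** No. On raw log-normal data with identical distributions at 12 versus 238, Welch rejects about 8% at log-SD 0.6 and 13% to 14% at log-SD 1.0. Rank-sum rejects 4.6% and 5.0%. With 60% zeros (an assumption), Welch rejects 10.1% and rank-sum 4.3%. For a doubled log-normal count (median 600 versus 300, log-SD 0.6), Welch detects 81% and rank-sum about 96%.

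**The case against.** - **A rank test need not be read as a test of means.** Many use it to ask whether one group tends to have higher values. That stands in part: as a test that the two distributions are identical, rejecting because spreads differ is not an error. But in the simulations neither group tends to be higher, so the distortion also applies to that looser question.
- **The plan is right to leave Student's t when variances differ.** This stands. At ratio 2 Student's t rejects 28.6%, so the rank test is an improvement, though not a sufficient one.
- **The SD ratios are assumed, and 12 versus 238 is the most uneven split in the cited range.** Both true. At 15% and 30% complications the distortion shrinks but remains, and the rule sends data to the rank test precisely when variances are judged unequal.
- **The word *count* is probably a slip.** Likely: the paragraphs otherwise match, and continuous variables are routed elsewhere in the same sentence. The two sections still need to agree, because an outsourced statistician may follow section 13.13.3 as written.
- **A reader might infer that Fisher's p-values would be badly wrong for counts, or that counts lose nearly all power.** Neither is supported. Fisher's test keeps its type I error, and the power loss is negligible for low counts and large only for wide-range ones.

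**Conclusion.** The concern holds as a minor but real fault in the analysis rules.

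- The signed rank test cannot apply to these independent groups. This needs no assumption.
- Read as rank-sum, the rule does not hold 5% as a test of location for approximately normal data with unequal variances: about 13.7% and 0.35% at assumed SD ratios of 2 and 0.5 with 12 versus 238, and at ratio 2 about 12% with 38 versus 212 and 9% with 75 versus 175. Welch stays near 5% throughout.
- The *count* versus *categorical* mismatch costs power, not validity, and only if taken literally for a wide-range count.

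A reader might infer that the main safety result is compromised. It is not: section 13.13.2 uses a one-sample proportion test, which this rule does not touch. The effect is confined to the secondary comparisons and the regression screen.

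**What to change.** In sections 13.1 and 13.13.3:

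1. Use Welch's t-test for approximately normal continuous variables, with no variance pre-test.
2. For skewed variables and wide-range counts such as laser coagulates, use the two-sample Wilcoxon rank-sum (Mann-Whitney) test, or Welch on the log scale where all values are positive. State in advance which variables these are. Do not use Welch on raw skewed counts.
3. Remove the reference to the signed rank test.
4. In section 13.13.3 replace *count variables* with *categorical variables*, to match section 13.1.

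Cost: a few sentences. Section 13.7 has the final statistical plan agreed before data lock, so the change fits there without touching conduct or sample size. Welch loses some power when variances are in fact equal: at 12 versus 238 and a 0.8 SD shift, 70% against 77% for Student's t.

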A powerful light source is required to illuminate the inside of the globe during surgery. For this purpose, a PMMA fiber is connected to the light source of the vitrectomy machine and guided into the eye.

Historically, a halogen light source was used. About 15 years ago, more powerful Xenon light sources became available and are still present in many vitrectomy devices. More recently, LED light sources became more popular. Also our present vitrectomy device (DORC EVA) is equipped with an LED light source.

Increasing light output is required when using ultra-small gauge surgery (27G), since the diameter of the light fiber is extremely thin. However, care must be taken by the surgeon to avoid light toxicity when the light source is held too close to the same area of the retina for too long. Retinal damage due to light toxicity after vitrectomy can have a major effect on the visual acuity of the patient.

In most light sources for vitrectomy surgery, the light is filtered, eliminating more bluish wavelengths to increase its safety.

5. Phaco ultrasound.

To remove an opacified lens from the eye (cataract), the lens needs to be emulsified in the eye. For this purpose, a small needle is used that is oscillating on an ultrasonic frequency. These oscillations emulsify the lens material, after which can be aspirated (using the aspiration system of the device). The DORC EVA has an analog driver board and operates at a frequency of 40 kHz.

6. Laser module.

To reattach the retina in case of retinal detachment, laser coagulates need to be placed around the breaks in the retina. For this purpose, a vitrectomy machine has a built-in laser module. A glass fiber is used to guide the laser light into the eye on the retina. Using the foot switch of the device, laser coagulates can be directed towards the desired location on the retina. The DORC EVA uses a 532 nm endo laser which has been the standard for ophthalmic use.

7. Silicone oil injection.

Not infrequently, the eye needs to be filled with silicone oil during surgery for retinal detachment. For this purpose, a system is present that drives the silicone oil from a (glass) syringe into the eye. The DORC EVA can drive (pre) filled syringes of silicon oil with a pressure up to 6 bars.

8. Silicone oil extraction.

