For removal of the silicone oil, a system is present that generates a high vacuum to remove the viscous oil from the eye through a small opening. The DORC EVA generates a vacuum up to 660 mmHg to remove the silicon oil.

9. Endodiathermy.

In case a hemorrhage occurs inside or outside of the eye, a diathermy probe can be connected to the vitrectomy device to coagulate the bleeding vessel. The DORC EVA operates at frequency of 1 Mhz to create the coagulation.

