6. OBJECTIVES

The primary objective and primary parameters are shown in the table below:

The main purpose of this study is to evaluate the intra-operative safety of a new surgical device.
	
Therefore, having no idea of the percentage of patients having complications, we make the hypothesis that minimum 5% of the patients will have complications. In order to make sure that we have at least 10 patients with complications, we plan recruit 250 patients in total in order to get at least 10 complications with EVA Nexus.
 
For this purpose, typical surgical parameters will be recorded during vitrectomy surgery:
 
 • Surgical indication • If combined phaco-surgery is performed: amount of phaco power used • Staining dyes (if used) • Amount of laser coagulates (if used) • Type of tamponade left in the eye: BSS+ liquid, air bubble, air, gas (type + concentration) or silicone oil (type) 
Specific adverse events that may occur during (phaco)vitrectomy will be recorded to assess the surgical safety ¹⁵⁻¹⁸: see list in Appendix A. This AE reporting is already present in the surgical report (KWS-Formasa) used for daily vitrectomy surgery using the DORC EVA device. The occurrence of these AE's during surgeries using the EVA Nexus will be compared to historical data retrieved from surgeries using the DORC EVA platform.
 
Device issues that caused some hindering during the surgery but that do not lead to an (S)AE, such as error messages/warnings that did occur, malfunctioning of supplies that required replacement etc. will be recorded.
 
See Appendix B for a full list, which is already part of our present surgical report (KWS-Formasa). The occurrence of these issues during surgeries using the EVA Nexus will be compared to historical data retrieved from surgeries using the DORC EVA platform.

---	---

The secondary objective and secondary parameters are shown in the table below:

Secondary objective	Secondary parameters
To evaluate the possible reduction of total surgical time.	The time that was required to prepare the EVA Nexus will be recorded (connecting of supplies + priming). During the study period, this time will also be recorded during surgeries performed with the DORC EVA device for comparison.

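### The exploratory predictive model does not exclude variables that can be a response to a complication, so it can list diathermy as a risk factor for the bleeding it was used to treat

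*Combined protocol and SAP*

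**What the plan says.** Sections 13.1 and 13.13.3 give the same modelling rule. After the group comparisons of patients with and without complications, a logistic or Poisson regression is run "in order to test a first predictive model". It uses backward selection, "starting with all variables associated with the target with a p-value lower than 0.1". On retention, section 13.1 says: "The final model will contain variables associated with the outcome with a p-value lower than 0.05".

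The data screened by complication status are the demographics and the secondary-objective data. One secondary objective in section 6 concerns the settings used in the operation: "The surgical parameters include a range of data collected on the following". Diathermy and laser are both on the list that follows.

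Section 5.1 says what diathermy is for: "In case a hemorrhage occurs inside or outside of the eye, a diathermy probe can be connected to the vitrectomy device to coagulate". What is coagulated is the vessel that bleeds. Appendix A counts hemorrhage from a retinal vessel, subretinal hemorrhage and subchoroidal hemorrhage among the vitrectomy complications.

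Section 7.2, footnote 3, records pre-operative conditions that affect the risk of adverse events, but no section names them as the model's candidates. Section 13.7 says a final statistical plan will be agreed before data lock and sets no restriction on candidates.

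**The concern.** A predictor has to be known, or at least fixed, before the event it predicts. Diathermy applied because a vessel bled comes after the event. The rule as written admits it all the same, and a true response to the complication will tend to pass a p-value screen because it really is associated with it. The model would then present a consequence as a risk factor.

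The forms shown would not let the analyst sort this out later. The Appendix A complications are tick-boxes without a time, and the adverse event form in Appendix C holds start and stop dates only. An intra-operative bleed and the diathermy used for it fall on the same day.

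What is at stake is a wrong risk factor in the statistician's report, which section 16.2 makes the source for the published results. The primary analysis compares one proportion with 30%, 15% and 5% and does not use this model.

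**Working it through.** **1. The plan's own figure.** Section 8.1 assumes about 5% complications and recruits 250 patients to obtain at least 10. Expected number: 250 × 0.05 = 12.5. The binomial probability of at least 10 is 0.805, and the central 95% range is 6 to 20 events. The figure of 250 is reasonable for its purpose, and 12 events is a fair working number.

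**2. The chain in the text.**
- Candidate: diathermy is among the secondary-objective parameters (section 6), which are compared by complication status (13.13.3).
- Reverse link: diathermy is used when a hemorrhage occurs (section 5.1).
- Outcome: hemorrhages are counted complications (Appendix A).
- Exclusion: no section removes it from the candidates.

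**3. How often it could matter.** The documents give none of the inputs below, so all are assumptions.
- *b* = background use of diathermy, coded used/not used: 10%, 30% or 50%.
- *f* = share of all complications that trigger diathermy: 0 to 30%.
- Diathermy has no causal effect and is the only candidate.
- 12 complicated patients versus 238 others.

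Use among complicated patients is b + f(1 − b). For b = 0.10 and f = 0.20 this is 0.10 + 0.20 × 0.90 = 0.28. The odds ratio produced by the response alone is (0.28/0.72)/(0.10/0.90) = 3.5. With f = 0.20 it is 1.8 at b = 0.30 and 1.5 at b = 0.50.

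Both binomials were enumerated exactly. Diathermy counts as kept if the two-sided Fisher p is below 0.1 and the logistic Wald p is then below 0.05; tables with a zero cell count as not kept. Probability of reaching the final model:

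| Background use | f = 0 | 5% | 10% | 20% | 30% |
|---|---|---|---|---|---|
| 10% | 0.034 | 0.097 | 0.194 | 0.452 | 0.701 |
| 30% | 0.025 | 0.046 | 0.076 | 0.172 | 0.318 |
| 50% | 0.033 | 0.036 | 0.043 | 0.072 | 0.124 |

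**4. Sensitivity to the event count.** At f = 20%, 6 events give 0.265, 0.074 and 0.000 for the three use rates, and 20 events give 0.592, 0.255 and 0.120.

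**5. Other candidates present.** A simulation of the plan's procedure used ten candidates, including an indication that doubles the odds of both complication and diathermy use (800 runs per cell, standard error up to 0.018). At f = 20% it gave 0.440, 0.196 and 0.099, close to the exact figures.

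**The case against.** The strongest reply is that nothing has been decided. The model is a first, exploratory one, done last, and section 13.7 leaves room to fix the candidate list before any analysis. That stands, and it is why the point is minor. It does not remove the point, because the rule as written has no timing limit and section 13.7 adds none.

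A second reply is that the large percentages need favourable inputs. This also stands. Appendix A names 18 specific complications, five of them in lens surgery, and patients having cataract surgery alone are eligible, so the share that triggers diathermy may be small. Section 5.1 also mentions bleeding outside the eye, which Appendix A does not list, so some diathermy use would be background. If diathermy is recorded as power or duration, the used/not-used calculation does not apply.

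A reader might infer three stronger points that the documents do not support:
- *Laser is an equal example.* It is weaker. Section 5.1 says "To reattach the retina in case of retinal detachment, laser coagulates need to be placed around the breaks in the retina", so laser is often part of the planned operation. An association with complications, which include iatrogenic retinal tear, may be confounding by indication. Section 6 records it as "Amount of laser coagulates (if used"), so the figures above do not apply.
- *Day-1 visual acuity and eye pressure will be candidates.* The relevant secondary objective is "a postoperative check of the eye at the day after the surgery" to find adverse events. The two measurements appear only as clinical tests in the flowchart, and only the most literal reading of the rule admits them.
- *The p-value selection inflates false positives.* In simulations with 10 to 20 assumed noise candidates at a 5% complication rate, about 4% of them were kept, slightly below plain testing at 5%. What selection does is exaggerate the odds ratios that are kept.

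**Conclusion.** The concern holds as a minor point about the exploratory model. Following sections 13.1 and 13.13.3 exactly can put diathermy in the final model as a risk factor when the complication caused its use. This conclusion comes from the text and needs no assumed rates. It takes the model's target to be complication status, which is the natural reading of the paragraph.

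The size is not known. Under the assumptions stated, the chance runs from about 4% to 70%, against about 3% with no link. It is large when background use is low and a sizeable share of complications trigger diathermy, and small when half of patients receive it anyway. The upper figure is a corner of the assumed range and should not be read as an estimate for this study.

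**What to change.** In sections 13.1 and 13.13.3:
- Limit the model's candidates to variables fixed before a complication can occur, for example planned procedure, indication, age, primary or repeat vitrectomy, and the pre-operative conditions of footnote 3 in section 7.2.
- Exclude diathermy and any other parameter or post-operative measurement that can be a response to a complication.
- List the candidates in the final statistical plan before data lock.
- Keep the intra-operative parameters in the planned group comparisons, and state there that they may be consequences of the complication. Such a p-value can still be reported, so the caution has to sit beside it.

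The cost is wording; no new data are needed. The downside is that the model no longer addresses intra-operative settings.

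Optional, as a modelling choice: with about 12 events, use a short prespecified set in a penalised logistic regression with bootstrap optimism correction, and report all coefficients. The correction is only partial. In a simulated check with five null candidates in a Firth model, an apparent AUC of 0.68 was corrected to 0.56 when the truth was 0.50.
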